14.7 Economic Analysis

Cost-effectiveness and cost-utility analyses will be performed based on respectively cost per life-year gained and cost per quality adjusted life year gained. The mean and standard deviation of cost-effectiveness and cost-utility ratio will be calculated and the bootstrap method will be used to derive the confidence intervals.

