2.1.1 Staging of Cervical Cancer

According to FIGO classification, there are four stages of cervical cancer (see Appendix III), which include the two most common histologic forms, squamous (~70%) and adenocarcinoma (~30%). Determination of staging relies primarily on clinical evaluation. “Early-stage” cancer is referred to stages IA2-IB1, which are both amenable to surgical treatment. Stage IA2 is based on the microscopic evaluation of the cervical lesion, usually removed by conization, and includes stromal invasion measuring < 5mm in depth and \leq 7mm in lateral extension. Stage IB1 refers to larger lesions that remain limited to the cervix and measure < 4 cm in maximum diameter. The 5-year survivals of patients with stage IA2 disease is 98% and for IB1 is 92%.

Radical hysterectomy with complete pelvic lymph node dissection is the standard treatment for “early-stage” disease. As the primary mode of tumour dissemination is via lymphatics, either proximally to the parametrial tissue or directly to the pelvic lymph node, node status is one of the most important prognostic factors. The rate of lymph node metastasis is approximately 5% in IA2 disease and 15% in stage IB1 disease. The 5-year survival in node negative IB1 patients is in the range of 96%, whereas it reduces to 79% in node positive patients.

“Low-risk” disease refers to patients with early-stage disease who have stage IA2 or stage IB1 and lesions measuring less than 2 cm in size with less than 50% stromal invasion [Schmeler, 2011]. In these patients, the risk of lymph node metastasis is < 5% and parametrial extension is < 1%. In the CCTG CX.5 / GCIG SHAPE trial, we will evaluate patients with low-risk disease. We hypothesize that less radical surgery (simple hysterectomy) will be associated with similar efficacy and less surgical morbidity than more radical surgery. According to local practices, we will include lymph node assessment through the less morbid approach of sentinel node mapping.

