2.7.4 Summary of Health Economic – Related Hypotheses

Given that simple hysterectomy may be associated with fewer short and long-term side effects, superior QoL and health-related utility scores may be associated with this procedure and may drive women’s decisions for treatment. Furthermore, it is possible that simple hysterectomy will be associated with use of fewer health care resources in the immediate postoperative period, including reduced hospital length of stay and need for management of postoperative complications. The economic hypotheses tested will thus include:

Hypothesis 1: We hypothesize that, in comparison with radical hysterectomy, health care-related resource utilization will be less in the simple hysterectomy group, as there will be fewer immediate postoperative and long-term management requirements. If non-inferiority of the primary and secondary efficacy outcomes is established, benefits resulting from a reduction in health care resource utilization will be associated with a favourable incremental cost-effectiveness ratio (cost per life-year gained).

Hypothesis 2: Building upon hypothesis #1, we further hypothesize that simple hysterectomy will be associated with fewer long-term adverse events and improved survivorship, and will thus be associated with superior health-related utility scores, resulting in an acceptable incremental cost-utility ratio (cost per quality adjusted life year gained).

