14.3 Sample Size and Duration of Study

It is estimated that the pelvic recurrence rate at 3 years for the radical hysterectomy is around 4% and we would consider simple hysterectomy is non-inferior to radical hysterectomy if its pelvic recurrence rate at 3 years is 8% or less. With 350 patient randomized to each of the two treatment arms, the study will have around 85% power to conclude the non-inferiority at 0.05 level when the pelvic recurrence rate at 3 years is the same in the two arms. Final analysis will be performed when the last patient randomized has been followed for 3 years.

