3.2 Secondary

Secondary objectives are to compare the following endpoints between two treatment arms:

- Pelvic relapse free survival (PRFS)
- Extra-pelvic relapse free survival (EPRFS)
- Relapse free survival (RFS)
- Overall survival (OS)
- Rate of sentinel node detection
- Rate of parametrial involvement
- Rate of surgical margin involvement
- Rate of pelvic nodes involvement
- Treatment-related adverse events
- Patient report outcomes including quality of life and measures of sexual health
- Cost-effectiveness and cost-utility

Note: The analysis plan to address the last objective, i.e., evaluation of cost-effectiveness and cost-utility will be developed at a later date.

4. Endpoints

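### The protocol's mean and SD of the cost-per-life-year ratio have no stable value when efficacy is equal, as the design assumes; for cost per QALY the problem depends on the size of the gain

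*Protocol*

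**What the plan says.** Protocol 14.7 is two sentences long. The analyses are "based on respectively cost per life-year gained and cost per quality adjusted life year gained". Then "The mean and standard deviation of cost-effectiveness and cost-utility ratio will be calculated", and "the bootstrap method will be used to derive the confidence intervals". It names no type of bootstrap interval, time horizon or rule for a denominator that is near zero or negative. It mentions no net benefit, cost-effectiveness plane or acceptability curve, and no other section supplies them.

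On the expected size of the effect:
- Protocol 14.3 computes power "when the pelvic recurrence rate at 3 years is the same in the two arms".
- Protocol 2.1.1 hypothesises that simple hysterectomy "will be associated with similar efficacy and less surgical morbidity than more radical surgery".
- Protocol 2.7.4, Hypothesis 1, expects lower resource use. Once non-inferiority is shown, it says, the benefits of this "will be associated with a favourable incremental cost-effectiveness ratio (cost per life-year gained"). Hypothesis 2 adds better utility scores, with no figure.

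SAP 3.2 lists cost-effectiveness and cost-utility among the secondary objectives but notes that the plan for "evaluation of cost-effectiveness and cost-utility will be developed at a later date".

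**The concern.** An incremental ratio is informative only when its denominator is clearly away from zero. In a non-inferiority trial with 5-year survival of 92% to 98% (Protocol 2.1.1), the life-year difference should be close to zero if the trial succeeds. That is exactly the situation in which Protocol 2.7.4 wants to quote a cost per life-year gained.

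Two problems follow. First, the mean and SD of the replicate ratios are governed by the few replicates whose denominator falls nearest zero, so they change with the random seed. Second, the sign of the ratio does not identify the result. A negative ratio can mean cheaper and better or dearer and worse; a positive one can mean dearer and better or cheaper and worse. An interval that orders replicates by the ratio places these cases on one scale.

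The stake is a secondary endpoint that Protocol 2.7.1 says could drive policy if non-inferiority is established.

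**Working it through.** **1. The design figure that sets the efficacy difference to zero.** Inputs from Protocol 14.2 and 14.3: 4% recurrence in both arms, 4-point margin, 350 per arm, one-sided 0.05.

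SE = sqrt(2 × 0.04 × 0.96 / 350) = 0.0148. Power = Φ(0.04/0.0148 − 1.645) = Φ(2.70 − 1.645) = 85.4%.

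This reproduces the stated 85%, so the planning assumption is a true difference of zero.

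**2. The life-year denominator.** Assumptions: exponential survival matched to the protocol's 5-year figures, a 3-year horizon, and an economic subset of 150 to 350 per arm. The protocol gives neither the horizon nor the subset size. SE of the difference = SD × sqrt(2/n).

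| 5-year survival | SD of life-years | SE, 350 per arm | SE, 150 per arm |
|---|---|---|---|
| 92% | 0.378 | 0.029 | 0.044 |
| 98% | 0.190 | 0.014 | 0.022 |

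With an expected difference of 0, about half of all replicates have a negative denominator, whatever the SE. A 5-year horizon widens the SE (0.031 to 0.060 at 350 per arm) but leaves the centre at zero.

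**3. The life-year ratio.** Further assumptions: incremental cost -2,000, cost SD 8,000, life-year SD 0.298 (5-year survival of 95%). Five sets of 5,000 normal replicates of incremental cost divided by incremental life-years, 350 per arm:

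| Set | Mean ratio | SD | 2.5th and 97.5th percentiles | Share with denominator < 0 |
|---|---|---|---|---|
| 1 | -49,490 | 7.1 million | -1.23 to +1.40 million | 0.511 |
| 2 | +140,395 | 10.3 million | -1.57 to +1.46 million | 0.511 |
| 3 | +238,575 | 12.1 million | -1.37 to +1.45 million | 0.496 |
| 4 | -1,030,754 | 76.6 million | -1.39 to +1.58 million | 0.498 |
| 5 | -126,674 | 9.1 million | -1.44 to +1.57 million | 0.495 |

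The mean changes sign between sets. The percentiles vary less, but they carry little meaning. The cost difference is 2,000/(8,000 × sqrt(2/350)) = 2,000/605 = 3.3 SE below zero, so nearly every replicate shows a saving. The two ends of the interval are then replicates with a saving and almost no life-year difference, separated only by the sign of that small difference.

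**4. Net monetary benefit on the same inputs.** At a threshold k, the expected value is k × 0 + 2,000 = 2,000, and SE = sqrt(2/350) × sqrt((k × 0.298)² + 8,000²). This is about 750, 1,280 and 2,340 at k = 20,000, 50,000 and 100,000. It is finite and has one direction of meaning.

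**5. The QALY ratio.** Assumptions: 3-year horizon and utility SD 0.15, so QALY SD = 3 × 0.15 = 0.45; costs as above. Three sets of 5,000 replicates each:

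| Utility gain per year | n per arm | Gain/SE | Mean ratio across sets | SD across sets |
|---|---|---|---|---|
| 0.01 | 350 | 0.88 | -171,800 to +18,700 | 1.7 to 7.5 million |
| 0.02 | 350 | 1.76 | -38,700 to +48,600 | 0.7 to 3.9 million |
| 0.03 | 350 | 2.65 | -26,900 to -25,000 | 84,000 to 162,000 |
| 0.05 | 150 | 2.89 | -16,100 to -15,400 | 42,500 to 78,000 |
| 0.05 | 350 | 4.41 | -14,200 to -14,000 | 5,800 to 6,200 |

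A second set of assumed inputs (cost -1,500, SE 600; QALY SE 0.03; five sets) agrees. At a gain of 0.10 (3.3 SE) the interval has settled at about -42,000 to -3,000 but the SD is still erratic. At 0.15 (5 SE) the mean is -10,300 to -10,500 and the SD 4,800 to 5,000 in every set.

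**The case against.** Four points can be made for the plan.

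- **The QALY denominator is not expected to be near zero.** Protocol 2.7.4 hypothesises better utilities, and Protocol 2.5.4 plans for differences of about half an SD on two patient-reported scales (7/13.5 and 5/10), though only 5/21 on the FSFI. These scales are not utilities. If utility did shift by half an SD, though, the gain would be 0.5/sqrt(2/350) = 6.6 SE from zero, or 0.5/sqrt(2/150) = 4.3 SE. This stands. A reader might infer that both ratios fail alike; the documents support that only for life-years.
- **The economic plan is not yet written.** A reader might infer that the 14.7 rule will pass into it. Nothing in SAP 3.2 says so, and nothing there withdraws 14.7 either. What stands is that 14.7 is the only specification in force and should not be copied forward.
- **The wording may be loose.** Mean and SD of the ratio could be shorthand for a point estimate and its standard error, and 14.7 does not say the bootstrap interval is a percentile interval. This is fair, but for life-years the standard error of the ratio is just as unstable, and any interval placed on the ratio itself meets the same sign problem.
- **The inputs are assumed.** Cost difference, cost SD, utility SD, horizon and subset size are not in the documents. The simulated values depend on them. The instability of the life-year ratio does not, because it follows from an expected denominator of zero.

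**Conclusion.** The point holds for cost per life-year gained. On the trial's own assumption of equal efficacy, the mean and SD of that ratio have no stable value, and an interval on it mixes results with opposite meanings. In the illustration the mean moved between about -1.03 million and +0.24 million with the seed alone.

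For cost per QALY the point is conditional on a gain that the protocol does not state: unstable within about 2 to 3 SE of zero, stable at about 4 to 5 SE or more. Since the plan cannot know in advance which applies, a summary that works in both cases is preferable.

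This concerns a stated method for a secondary endpoint, not missing detail. It has no bearing on the primary non-inferiority conclusion or on safety.

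**What to change.** In Protocol 14.7, or in the deferred economic plan in place of 14.7's wording, drop the mean and SD of the ratios and report:

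- incremental cost and incremental effect, each with an interval;
- the ratio of mean differences as a point estimate only, and only where its sign and denominator make it interpretable;
- incremental net monetary benefit with a bootstrap interval at pre-stated willingness-to-pay values;
- the cost-effectiveness plane and the acceptability curve.

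All of these come from the same bootstrap replicates, so no extra data are needed. At the same time, state the time horizon and settle the effectiveness measure: Protocol 2.7.2 uses life expectancy free of pelvic relapse, whereas 2.7.4 and 14.7 use life-years gained.

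The cost is that willingness-to-pay values must be agreed before the analysis. If the change is made in 14.7 it also needs a protocol amendment; the deferred plan avoids that and is the easier place.

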15.0 PUBLICATION POLICY

15.1 Authorship of Papers, Meeting Abstracts, Etc

15.1.1 The results of this study will be published. Normally, authorship includes the naming of individual authors. As per CCTG authorship policies, publication of the final analysis of the primary outcome includes:

- The first author will generally be the chair of the study.
- The second author will normally be the CCTG Senior Investigator and the last (Senior) author will be the CCTG Gynecology Committee Chair. The CCTG Authorship policy indicates criteria that must be satisfied by the Disease Site Committee Chair in order to be recognized as Senior Author. When the time frame and duration of a study preclude the Site Chair from meeting these criteria, the CCTG Senior Investigator will normally be the senior Author.
- The CCTG Senior Biostatistician will normally be the second last (Co-senior) author.
- Additional authors, as allowed by journal policies, will be those who have made the most significant contribution to the overall success of the study. This contribution will be assessed, in part but not entirely, in terms of patients enrolled and will be reviewed at the end of the trial by the study chair. Normally, these authors will include those investigators forming the CCTG Trial Committee.
- Each participating centre is to identify a reference pathologist. **The reference pathologists are considered contributing investigators and will be identified as individuals in relevant publications.** Typically such recognition is placed within an appendix, including supplementary online appendices.
- In the event of a separate paper dealing with the quality of life outcomes, the first author will generally be the Quality of Life Coordinator on the trial committee.
- In the event of a separate paper dealing with the economic outcomes, the first author will generally be the Committee on Economic Analysis liaison on the trial committee.

For Intergroup trials, such as CX.5, a member of a cooperative group that has contributed at least 5% to the total accrual will be included. An additional member from that group will be included for each additional increase of 10% to the total accrual (i.e. 2 authors for > 15%, 3 authors for > 25%, etc.). Each cooperative group will be asked to identify the author(s) to be named.

For separate papers dealing with secondary endpoints, the first author will generally be the CCTG investigator named as responsible for that endpoint (e.g. QoL, economics, etc.). For subset analyses, the first author will be assigned on a prospective basis in a manner consistent with CCTG's policies, which state: *"The nature of a cooperative group requires that collaborations be nurtured. The most prestigious of authorship positions (First Author, Senior Author) must therefore be appropriately distributed among the individuals eligible for these positions across the reports associated with a project. Similarly, positions of Other Contributing Authors should be distributed to account for contributions to a project, including trial accrual."* These principles include the recognition of investigators based with collaborating cooperative groups.

15.1.2 In an appropriate footnote, or at the end of the article, the following statement will be made:

"A study coordinated by the Canadian Cancer Trials Group. Participating investigators included: (a list of the individuals who have contributed patients and their institutions)."

15.2 Responsibility for Publication

It will be the responsibility of the Study Chair to write a manuscript describing the results of the study within a reasonable time of its completion. If, after a period of six months following the analysis of study results, the draft is not substantially complete, the CCTG Central Office reserves the right to make other arrangements to ensure timely publication.

15.2.1 Dissemination of Trial Results

CCTG will inform participating investigators of the primary publication of this trial. The complete journal reference and, if where publicly available, the direct link to the article will be posted on the Clinical Trial Results public site of the CCTG web site (<http://www.ctg.queensu.ca>).

15.3 Submission of Material for Presentation or Publication

Material may not be submitted for presentation or publication without prior review by the CCTG Senior Investigator, Senior Biostatistician, Study Coordinator, and approval of the Study Chair. Supporting groups and agencies will be acknowledged.

16.0 ETHICAL, REGULATORY AND ADMINISTRATIVE ISSUES

16.1 Regulatory Considerations

All institutions in Canada must conduct this trial in accordance with International Conference on Harmonization-Good Clinical Practice (ICH-GCP) Guidelines.

All institutions outside of Canada should refer to their group-specific appendix for additional instructions regarding regulatory requirements.

16.2 Inclusivity in Research

CCTG does not exclude individuals from participation in clinical trials on the basis of attributes such as culture, religion, race, national or ethnic origin, colour, mental or physical disability (except incapacity), sexual orientation, sex/gender, occupation, ethnicity, income, or criminal record, unless there is a valid reason (i.e. safety) for the exclusion.

In accordance with the Declaration of Helsinki and the Tri-Council Policy Statement (TCPS), it is the policy of CCTG that vulnerable persons or groups will not be automatically excluded from a clinical trial (except for incompetent persons) if participation in the trial may benefit the patient or a group to which the person belongs.

However, extra protections may be necessary for vulnerable persons or groups. It is the responsibility of the local investigator and research ethics board (REB) to ensure that appropriate mechanisms are in place to protect vulnerable persons/groups. In accordance with TCPS, researchers and REBs should provide special protections for those who are vulnerable to abuse, exploitation or discrimination. As vulnerable populations may be susceptible to coercion or undue influence, it is especially important that informed consent be obtained appropriately.

Centres are expected to ensure compliance with local REB or institutional policy regarding participation of vulnerable persons/groups. For example, if a vulnerable person/group would be eligible for participation in a CCTG clinical trial under this policy but excluded by local policy, it is expected that they would not be enrolled in the trial. It is the centre's responsibility to ensure compliance with all local SOPs.

It is CCTG's policy that persons who cannot give informed consent (i.e. mentally incompetent persons, or those physically incapacitated such as comatose persons) are not to be recruited into CCTG studies. It is the responsibility of the local investigator to determine the subject's competency, in accordance with applicable local policies and in conjunction with the local REB (if applicable).

Subjects who were competent at the time of enrolment in the clinical trial but become incompetent during their participation do not automatically have to be removed from the study. When re-consent of the patient is required, investigators must follow applicable local policies when determining if it is acceptable for a substitute decision maker to be used. CCTG will accept re-consent from a substitute decision maker. If this patient subsequently regains capacity, the patient should be re-consented as a condition of continuing participation.

16.3 Obtaining Informed Consent

It is expected that consent will be appropriately obtained for each participant/potential participant in an CCTG trial, in accordance with ICH-GCP section 4.8. The centre is responsible for ensuring that all local policies are followed.

Additionally, in accordance with GCP 4.8.2, CCTG may require that participants/potential participants be informed of any new information that may impact a participant's/potential participant's willingness to participate in the study.

Based upon applicable guidelines and regulations (Declaration of Helsinki, ICH-GCP), a participating investigator (as defined on the participants list) is ultimately responsible, in terms of liability and compliance, for ensuring informed consent has been appropriately obtained. CCTG recognizes that in many centres other personnel (as designated on the participants list) also play an important role in this process. In accordance with GCP 4.8.5, it is acceptable for the Qualified Investigator to delegate the responsibility for conducting the consent discussion.

CCTG requires that each participant sign a consent form prior to their enrollment in the study to document her willingness to take part. CCTG may also require, as indicated above, that participants/potential participants be informed of new information if it becomes available during the course of the study. In conjunction with GCP 4.8.2, the communication of this information should be documented.

CCTG allows the use of translators in obtaining informed consent. Provision of translators is the responsibility of the local centre. Centres should follow applicable local policies when procuring or using a translator for the purpose of obtaining informed consent to participate in a clinical trial.

In accordance with ICH-GCP 4.8.9, if a subject is unable to read then informed consent may be obtained by having the consent form read and explained to the subject.

For institutions outside of Canada, please refer to your group-specific appendix for additional detailed instructions regarding informed consent.

16.4 Discontinuation of the Trial

If this trial is discontinued for any reason by the CCTG all centres will be notified in writing of the discontinuance and the reason(s) why. If the reason(s) for discontinuance involve any potential risks to the health of patients participating on the trial or other persons, the CCTG will provide this information to centres as well.

If this trial is discontinued at any time by the centre (prior to closure of the trial by the CCTG), it is the responsibility of the qualified investigator to notify the CCTG of the discontinuation and the reason(s) why.

Whether the trial is discontinued by the CCTG or locally by the centre, it is the responsibility of the qualified investigator to notify the local Research Ethics Board and all clinical trials subjects of the discontinuance and any potential risks to the subjects or other persons.

